### 5.1.1.2 Study Phases for Each Subject

Each subject enrolled in this study will undergo the following study phases/visits: Clinical Screening, Treatment Phase, End-of-Treatment (EOT) Visit, Safety Follow-up (30-day Safety Follow-up Visit and 90-day Phone Call), and Long-term Follow-up. Further details are provided in [Figure 5-2](#) and [Section 7.1](#).

**Figure 5-2 Study Phases per Subject**

## 5.1.2 Investigational Medicinal Product Administration and Schedule

The Schedule of Assessment for the study, including the treatment schedule, is provided in [Table 1-1](#) (for all subjects receiving avelumab once every 2 weeks); [Table 1-2](#) (for 6 subjects receiving avelumab once a week for the first 12 weeks followed by once every 2 weeks).

### 5.1.2.1 Avelumab

Subjects will receive an IV infusion of avelumab (over 1 hour [- 10 minutes/+ 20 minutes, ie, 50 to 80 minutes]) once every 2 weeks or every week (10 mg/kg once weekly cohort) for the first 12 weeks, then starting with Week 13, once every 2 weeks thereafter. The dose of avelumab will be calculated based on the weight of the subject determined within 72 hours prior to the day of drug administration. The dose of avelumab used for the previous administration can be repeated if the change in subject's weight is < 10% than the weight used for the last dose calculation. If the weight change is ≥10%, the intended dose should be recalculated.

In order to mitigate infusion-related reactions, a premedication regimen of 25 to 50 mg diphenhydramine and 500 to 650 mg acetaminophen (IV or oral equivalent) is mandatory approximately 30 to 60 minutes prior to the first 4 doses of avelumab. Premedication should be administered for subsequent avelumab doses based upon clinical judgment and presence/severity of prior infusion reactions. This regimen may be modified based on local treatment standards and guidelines, as appropriate. However, the prophylactic use of systemic corticosteroids is not permitted. (See [Section 6.4](#)).

Formulation and packaging information for avelumab are provided in [Sections 6.1](#) and [6.6](#), respectively.

### 5.1.2.1.1 Avelumab Starting Dose

The starting dose of avelumab in Chinese subjects, ie, subjects in the first dose escalation cohort, will be 3 mg/kg.

### 5.1.2.1.2 Dose Escalation Scheme

Subjects will receive avelumab by IV infusion over 1 hour once every 2 weeks. Dose escalation of avelumab will be performed according to the following dose levels, representing a 3.3 or 2 times increase at each escalation. Each subject will receive a fixed dose of avelumab according to their allocated dose level:

- 3 mg/kg
- 10 mg/kg
- 20 mg/kg

The dose escalation criteria are as follows:

For each dose level, DLTs (as defined in Section 7.4.1.1) will be assessed during the 21 days after administration of avelumab. The criteria for moving from 3 mg/kg to 10 mg/kg of avelumab is if no subject experiences a DLT in the first 3 subjects. No additional 3 subjects will be enrolled. If 1 out of the first 3 subjects in the 3 mg/kg cohort experiences a DLT, this cohort will be expanded to 6 subjects. If  $\geq 2$  out of 3 or 6 subjects in the 3 mg/kg cohort experience a DLT, the study will be placed on hold. See also Section 2.1.

[figure not shown]
In the 10 mg/kg once every 2 weeks cohort, 6 slots will be opened at the same time for competitive enrolment of 6 subjects. If less than 2 out of the 6 subjects in this cohort experience a DLT, the dose of 10 mg/kg will be considered safe in Chinese subjects. If 2 or more subjects experience a DLT, the study will be placed on hold.

After completion of the 10 mg/kg once every 2 weeks cohort, the dose of avelumab will be escalated to 20 mg/kg once every 2 weeks in order to characterize the safety and PK of avelumab at a higher dose level. The criteria for moving from 10 mg/kg to 20 mg/kg of avelumab is if less than 2 out of 6 subjects experience a DLT at the 10 mg/kg dose level (once every 2 weeks cohort). Staggered “3 + 3” enrolment will be used for the 20 mg/kg cohort. If no subject experiences a DLT in the first 3 subjects, the avelumab dose level at 20 mg/kg once every 2 weeks will be regarded as safe in Chinese subjects; the additional 3 subjects will be enrolled to fill up the cohort for PK evaluation, but they will not be subjected to further DLT evaluation.

If 1 subject in the first 3 subjects experiences a DLT (confirmed by SMC only), an additional 3 subjects will be enrolled. If less than 2 out of the 6 subjects experience a DLT, the dose of 20 mg/kg will be considered safe in Chinese subjects. If  $\geq 2$  out of 3 or 6 subjects experience a DLT, the 20 mg/kg cohort will be put on hold (the decision will be made by SMC).

A schematic of the dose escalation algorithm is presented in [Figure 5-3](#).

**Figure 5-3 Dose Escalation Algorithm for Doses up to 20 mg/kg of Avelumab**

DLT: dose-limiting toxicity; Q2W: every 2 weeks; QW: every week.

At the conclusion of the 21-day DLT observation period for each cohort (excluding 10 mg/kg once weekly cohort), a data review will be conducted. The SMC (including Principal Investigators), is responsible for making dose escalation decisions. The SMC will decide whether or not to escalate the dose of avelumab to the next level, or whether an interim dose level will be added by reviewing the safety data after all subjects of a cohort have completed the DLT observation period (see Section 2.1 and SMC Charter).

### 5.1.3 Dose Modification and Adverse Drug Reactions Requiring Treatment Discontinuation

#### Dose Modification for Avelumab

Each subject will stay on the avelumab dose level assigned in the study unless the treatment needs to be stopped. Dosing modifications (changes in infusion rate) and dose delays are described in Sections 6.5.4 and 6.5.5. There will be no dose reductions.

Treatment with avelumab can be skipped for a delay of up to 4 weeks from the previous dose for any non-related AEs, laboratory abnormalities, or intercurrent illness, which in the judgment of the Investigator warrants delaying the dose of study medication. If dosing is delayed more than 4 weeks, treatment may be resumed only after consultation with the study Medical Monitor. Any delay in dosing in excess of 12 weeks is not permitted.

### 5.1.3.1 Adverse Drug Reactions Requiring Treatment Discontinuation or Modifications

The following adverse drug reactions (ADRs) require permanent discontinuation or treatment modification of avelumab treatment:

- Any Grade 4 ADRs: permanently discontinue avelumab except for laboratory values out of normal range that do not have any clinical correlation.
- Any Grade 3 ADRs:
  - Withhold avelumab except for laboratory values out of normal range that do not have any clinical correlate.
  - Permanently discontinue avelumab if toxicity does not resolve to Grade  $\leq 1$  or baseline within 12 weeks of last administration or if the same Grade 3 toxicity recurs (consider consult with the medical monitor before permanently discontinuing the treatment).
- Infusion should not be given if ECOG performance status is  $\geq 3$  on the day of study treatment administration. Treatment should be discontinued if ECOG performance status has not improved to  $\leq 2$  by the next scheduled treatment administration.
- Any Grade 2 ADRs should be managed as follows:
  - Infusion should not be given in case of ongoing Grade 2 ADR on the day of study treatment administration.
  - Treatment can be resumed according to original schedule\* once ADR resolved to Grade  $\leq 1$ . Up to 2 subsequent study drug doses may be omitted. If more than 2 doses are skipped, treatment may be resumed after consultation with the Medical Monitor.

\*Original schedule is defined as “the dosing schedule calculated according to first dose”.

If dosing is delayed more than 4 weeks, treatment may be resumed after consultation with the study Medical Monitor. Any delay in dosing in excess of 12 weeks is not permitted.

Infusion-related reactions and irAEs should be handled according to the guidelines provided in Sections 6.5.5.1 and 6.5.5.2, respectively.

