### 6.5.5.2 Immune-related Adverse Events

Since inhibition of PD-L1 stimulates the immune system, irAEs may occur. Treatment of irAEs is mainly dependent upon severity (ie, NCI-CTCAE grade):

- Grade 1 to 2: treat symptomatically or with moderate dose steroids, more frequent monitoring.
- Grade 1 to 2 (persistent): manage similar to high grade AE (Grade 3 to 4).

- Grade 3 to 4: treat with high-dose corticosteroids.

Treatment of irAEs should follow the guidelines provided in [Table 6-2](#).

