
Grade 3 to 4 Grade 3: Covering > 30% body surface area; Grade 4: Life-threatening consequences
	
Withhold avelumab for Grade 3. Permanently discontinue for Grade 4 or recurrent Grade 3 Consider skin biopsy Dermatology consult 1.0 to 2.0 mg/kg/day prednisone or equivalent Add prophylactic antibiotics for opportunistic infections
	
If improves to Grade 1: Taper steroids over at least 1 month; resume avelumab therapy following steroids taper (for initial Grade 3)

Pulmonary irAEs		
Grade of Pneumonitis (NCI-CTCAE v4.03)	Initial Management	Follow-up Management

Grade 1 Radiographic changes only
	
Consider withholding avelumab therapy Monitor for symptoms every 2 to 3 days Consider Pulmonary and Infectious Disease consults
	
Re-assess at least every 3 weeks If worsens: treat as Grade 2 or Grade 3 to 4

Grade 2 Mild to moderate new symptoms
	
Withhold avelumab therapy Pulmonary and Infectious Disease consults Monitor symptoms daily, consider hospitalization 1.0 to 2.0 mg/kg/day prednisone or equivalent Add prophylactic antibiotics for opportunistic infections Consider bronchoscopy, lung biopsy
	
Re-assess every 1 to 3 days If improves: When symptoms return to Grade ≤ 1, taper steroids over at least 1 month, and then resume avelumab therapy following steroids taper If not improving after 2 weeks or worsening: treat as Grade 3 to 4

Grade 3 to 4 Grade 3: Severe new symptoms; New/worsening hypoxia; Grade 4: life-threatening
	
Permanently discontinue avelumab therapy Hospitalize Pulmonary and Infectious Disease consults 1.0 to 2.0 mg/kg/day prednisone or equivalent Add prophylactic antibiotics for opportunistic infections Consider bronchoscopy, lung biopsy
	
If improves to Grade ≤ 1: taper steroids over at least 1 month If not improving after 48 hours or worsening: add additional immunosuppression (eg, infliximab, cyclophosphamide, iv immunoglobulin, or mycophenolate mofetil)

Hepatic irAEs		
Grade of Liver Test Elevation (NCI-CTCAE v4.03)	Initial Management	Follow-up Management

Grade 1 Grade 1 AST or ALT > ULN to 3.0 x ULN and/or total bilirubin > ULN to 1.5 x ULN
	
Continue avelumab therapy
	
Continue liver function monitoring If worsens: treat as Grade 2 or 3 to 4

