Grade 2 AST or ALT > 3.0 to ≤ 5 × ULN and/or total bilirubin > 1.5 to ≤ 3 × ULN	Withhold avelumab therapy Increase frequency of monitoring to every 3 days	If returns to Grade ≤ 1: Resume routine monitoring; resume avelumab therapy If elevation persists > 5 to 7 days or worsens: Treat as Grade 3 to 4
Grade 3 to 4 AST or ALT > 5 × ULN and /or total bilirubin > 3 × ULN	Permanently discontinue avelumab therapy Increase frequency of monitoring to every 1 to 2 days 1.0 to 2.0 mg/kg/day prednisone or equivalent Add prophylactic antibiotics for opportunistic infections Consult gastroenterologist/hepatologist Consider obtaining MRI/CT scan of liver and liver biopsy if clinically warranted	If returns to Grade ≤ 1: taper steroids over at least 1 month If does not improve in > 3 to 5 days, worsens or rebounds: add mycophenolate mofetil 1 g twice daily If no response within an additional 3 to 5 days, consider other immunosuppressants per local guidelines
Renal irAEs		
Grade of Creatinine Increased (NCI-CTCAE v4.03)	Initial Management	Follow-up Management
Grade 1 Creatinine increased > ULN to 1.5 × ULN	Continue avelumab therapy	Continue renal function monitoring If worsens: Treat as Grade 2 to 3 or 4
Grade 2 to 3 Creatinine increased > 1.5 and ≤ 6 × ULN	Withhold avelumab therapy Increase frequency of monitoring to every 3 days 1.0 to 2.0 mg/kg/day prednisone or equivalent. Add prophylactic antibiotics for opportunistic infections Consider renal biopsy	If returns to Grade ≤ 1: Taper steroids over at least 1 month, and resume avelumab therapy following steroids taper. If worsens: Treat as Grade 4.
Grade 4 Creatinine increased > 6 × ULN	Permanently discontinue avelumab therapy Monitor creatinine daily 1.0 to 2.0 mg/kg/day prednisone or equivalent. Add prophylactic antibiotics for opportunistic infections Consider renal biopsy Nephrology consult	If returns to Grade ≤ 1: Taper steroids over at least 1 month
Cardiac irAEs		
Myocarditis	Initial Management	Follow-up Management

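### For a drug-related liver or creatinine rise without a clinical correlate, Section 5.1.3.1 and Table 6-2 prescribe different actions, and nothing usable at the time of treatment says which one governs

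*Protocol*

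**What the plan says.** Protocol Section 5.1.3.1 sets rules by grade for ADRs, which Section 7.4.1.1 defines as any AE suspected to be related to avelumab.

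- Grade 3, first step: "Withhold avelumab except for laboratory values out of normal range that do not have any clinical correlate".
- Grade 3, second step: permanent discontinuation if the toxicity has not resolved to Grade 1 or baseline "within 12 weeks of last administration or if the same Grade 3 toxicity recurs". This step has no laboratory exemption.
- Grade 4: "Any Grade 4 ADRs: permanently discontinue avelumab except for laboratory values out of normal range that do not have any clinical correlation".
- Closing sentence: "Infusion-related reactions and irAEs should be handled according to the guidelines provided in Sections 6.5.5.1 and 6.5.5.2, respectively".

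Section 6.5.5.2 introduces Table 6-2 with "Treatment of irAEs should follow the guidelines provided in" that table. The hepatic rows grade the liver test result itself. At AST or ALT above 5 x ULN, or total bilirubin above 3 x ULN, the action begins "Permanently discontinue avelumab therapy Increase frequency of monitoring to every 1 to 2 days". At Grade 2 avelumab is withheld, and then "If elevation persists > 5 to 7 days or worsens: Treat as Grade 3 to 4". The renal rows grade creatinine alone: withholding with steroids at Grade 2 to 3, permanent discontinuation at Grade 4. Neither set of rows exempts values that lack a clinical correlate.

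**The concern.** A site faced with an asymptomatic, related liver or creatinine rise must decide whether to dose, hold or stop for good. The two sections can answer differently for the same number. That is first a subject-safety and consistency matter, because sites may treat identical values in opposite ways. It also reaches the analysis in two places. One is whether a subject receives dose 2 and stays evaluable for the primary DLT endpoint. The other is whether continuing after a Grade 4 laboratory value is recorded as an important protocol deviation.

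**Working it through.** There is no planned figure to reproduce, so the check sets the rules side by side. Grade limits are those of SAP Section 18.3. Every row assumes a related value with no clinical correlate.

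| Value | Section 5.1.3.1 | Table 6-2 |
|---|---|---|
| ALT >3 to 5 x ULN (Grade 2) | No infusion while ongoing; resume at Grade 1 or less | Withhold; if it lasts beyond 5 to 7 days or worsens, use the Grade 3 to 4 row (permanent stop) |
| ALT >5 to 20 x ULN (Grade 3) | Exempt from withholding; permanent stop only if unresolved at 12 weeks or recurrent | Permanent stop |
| ALT >20 x ULN (Grade 4) | Exempt from permanent stop | Permanent stop |
| Creatinine >3 to 6 x ULN (Grade 3) | As for Grade 3 ALT | Withhold, with steroids |
| Creatinine >6 x ULN (Grade 4) | Exempt from permanent stop | Permanent stop |

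The initial action differs at Grades 3 and 4. At Grade 2 both sections stop dosing at first, and for liver values they part only if the rise persists or worsens. Within 5.1.3.1 itself, the Grade 2 rule has no laboratory exemption although the Grade 3 withholding rule has one.

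**Does the text choose between the columns?** The routing sentence does so once an event has been called an irAE. The remaining question is what makes a laboratory-only related rise an irAE.

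- Section 7.4.1.1 defines an ADR by relatedness alone and does not separate immune from non-immune events.
- Section 7.4.3 refers LFT elevations needing extra draws to Section 6.5.5.2 and Table 6-2, with no irAE condition.
- The DLT definition in Section 7.4.1.1 names only 5.1.3.1 as the place where ADRs requiring permanent discontinuation are described.
- Table 6-2 has a step for ruling out an immune cause for myocarditis and for other suspected irAEs. The hepatic and renal rows have none.
- The irAE flag in SAP Section 18.2 requires corticosteroids, immunosuppressants or hormonal therapy to have been given already, so it cannot guide the treatment decision.

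**Effect on the DLT Analysis Set.** In Table 1-1 the first scheduled on-treatment chemistry panel is Day 15, the dose 2 visit, and Section 7.4.3 requires results to be reviewed before dosing. Take a related Grade 3 ALT rise found that day.

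1. Under the 5.1.3.1 exemption, dose 2 is given and the subject remains evaluable.
2. Under Table 6-2, avelumab stops. If the rise does not resolve to Grade 1 or less in under 7 days after management starts, it is a DLT, subject to the Safety Monitoring Committee's confirmation. A subject who stops for a DLT stays in the set (Section 8.4).
3. Under Table 6-2 with resolution in under 7 days, the Grade 3 LFT exception applies and there is no DLT. The subject has had one dose, does not meet the dose-determination requirement of Section 5.1.1.1, drops out of the set and may be replaced.

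Only path 3 changes the set. The LFT exception does not extend to Grade 4. One subject is 1/6 = 17% or 1/3 = 33% of a cohort of 6 or 3.

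**Deviation coding.** Protocol Section 5.5.2 lists any ADR of Grade 4 or above as a withdrawal criterion and cross-refers to 5.1.3.1. SAP PDEV07 counts continuing after such an ADR as an important deviation. It cites 5.5.2 but does not repeat the exemption, and a programmed check is among its listed methods.

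**The case against.** The strongest reply is that 5.1.3.1 is a general rule with a specific carve-out. An irAE goes to Table 6-2 and any other ADR stays in 5.1.3.1, so the two never govern the same classified event. Classification is ordinarily the investigator's task, and the protocol gives some help. Section 6.5.4 names autoimmune hepatitis and glomerulonephritis among the events to watch for, and Section 7.4.1.1 treats any suspected irAE as an event of special interest. Section 7.4.1.1 also keeps many isolated laboratory findings from being AEs at all, and hence from being ADRs.

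Much of this stands. A reader might infer a flat contradiction; the routing sentence rules that out. A reader might infer that 5.1.3.1 lets a Grade 3 laboratory rise continue indefinitely; the unresolved-or-recurrent step rules that out. PDEV07 can reach the exemption through 5.5.2 and also lists medical review.

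The reply does not supply the missing assignment rule. The pointers in 7.4.3 and in the DLT definition lead to different sections. The AE test does not settle it either: one way a laboratory finding becomes an AE is by leading to discontinuation, which is the action in dispute. The exemption in 5.1.3.1 itself presupposes that laboratory-only ADRs occur.

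**Conclusion.** The concern holds as a gap between two pathways. For a related liver or creatinine rise without a clinical correlate, the initial action at Grades 3 and 4 depends on a classification that the documents do not tell a site how to make when the dose is due. For ALT above 5 x ULN the outcomes are continued dosing or a permanent stop.

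A reader might infer that the primary DLT endpoint is broadly at risk. The documents do not support that: at the scheduled panels, the set changes only for a Grade 3 liver enzyme rise stopped under Table 6-2 before dose 2 and resolved in under 7 days, and that subject may be replaced. The 17% and 33% are cohort fractions for one subject, not expected frequencies; the documents give no rate for such rises.

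The conclusion assumes the event is judged related and counts as an AE. It takes no view on which clinical rule is right.

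**What to change.** Reconcile Protocol Sections 5.1.3.1, 5.5.2, 7.4.1.1 (DLT definition) and 7.4.3, the hepatic and renal rows of Table 6-2, and SAP Section 18.1.

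- In 5.1.3.1, state whether the laboratory exemption applies to the hepatic and renal parameters of Table 6-2, and which section governs a laboratory-only related rise.
- Make the cross-references in 7.4.1.1 and 7.4.3 point to that same rule.
- Make PDEV07 carry the same exemption as 5.1.3.1 and 5.5.2, so that a site following the protocol is not recorded as deviating.

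The choice of rule belongs to the sponsor. The cost is amendment and SAP wording, with no extra data, visits or staff.

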## 5.2 Discussion of Study Design

Although the MTD of avelumab as a single agent has been evaluated in 2 other Phase I studies (the global EMR100070-001 study and the Japanese EMR100070-002 study), the Health Authority in China requires that a dedicated study be performed to assess the safety, tolerability, and PK of avelumab in Chinese subjects. Thus, this Phase I/Ib, open-label, dose-escalation study is designed to assess the PK, safety, tolerability, and also exploring efficacy of avelumab in Chinese adults with locally advanced unresectable or metastatic solid tumors who have failed standard of care or for whom no standard of care exists.

### 5.2.1 Study Population

The target population comprises subjects with metastatic or locally advanced unresectable solid tumors who fail standard therapy or subjects for whom no standard therapy exists. Candidate tumor types in the study may include tumors with known reports of PD-L1 overexpression, such as MCC, NSCLC, gastric/gastroesophageal junction cancer, esophageal cancer, urothelial cancer, melanoma, castration-resistance prostate cancer, ovarian cancer, head and neck squamous cell carcinoma, renal cell carcinoma, adenoid cystic carcinoma, mesothelioma, liver cancer (hepatocellular carcinoma and biliary), nasopharyngeal cancer, or other tumor types that are considered appropriate by Investigators.

### 5.2.2 Avelumab Dose Selection

Two Phase I studies (the global EMR100070-001 study and the Japanese EMR100070-002 study) have already evaluated the MTD of avelumab and established the recommended Phase II dose (RP2D) of avelumab as a single agent as 10 mg/kg every 2 weeks. The 3 dose levels selected for this study (3, 10, and 20 mg/kg of avelumab) are the same as those studied in the EMR100070-001, and -002 studies. At the dose level of 10 mg/kg, avelumab will be evaluated in 2 dose regimens: 10 mg/kg once every 2 weeks, and 10 mg/kg every week for 12 weeks, followed by transition to once every 2 weeks at Week 13 for the remainder of the treatment period. The rationale for the regimen of 10 mg/kg once weekly is described in Section 3.3.1. This will allow the safety, tolerability and PK of all 3 dose levels (2 regimens at the level of 10 mg/kg) of avelumab to be compared across studies, including with respect to ethnic sensitivity.

Furthermore, within the dose range of 1 mg/kg to 20 mg/kg, avelumab was shown to be well tolerated and is deemed to have an acceptable safety profile. In this first study in Chinese subjects with solid tumor there is added value in evaluating 20 mg/kg of avelumab with respect to safety and tolerability, and hence to provide a margin for the likely RP2D at 10 mg/kg in future development. In addition, with 3 dose levels ranging from 3 mg/kg to 20 mg/kg, a more informative assessment of the dose-exposure-response relationship may be obtained.

